9.4 Relationship to the Study Intervention

All adverse events (AEs) must have their relationship to study intervention assessed by the clinician who examines and evaluates the participant based on temporal relationship and his/her clinical judgment. The degree of certainty about causality will be graded using the categories below. In a clinical trial, the study product must always be suspect.

- Related The AE is known to occur with the study intervention, there is a reasonable possibility that the study intervention caused the AE, or there is a temporal relationship between the study intervention and event. Reasonable possibility means that there is evidence to suggest a causal relationship between the study intervention and the AE.
- Possibly Related There is some evidence to suggest a causal relationship (e.g., the event occurred within a reasonable time after administration of the study device). However, other factors may have contributed to the event (e.g., the participant's clinical condition, other concomitant events). Although an AE may rate only as "possibly related" soon after discovery, it can be flagged as requiring more information and later be upgraded to "Related."
- Not Related There is not a reasonable possibility that the administration of the study intervention caused the event, there is no temporal relationship between the study intervention and event onset, or an alternate etiology has been established.

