4.2 Study Endpoints

4.2.1 Primary Safety Endpoints

Composite of new major device related adverse events (MAEs) at 30 days post EchoMark implantation, as adjudicated by the Clinical Events Committee (CEC) including:

- Device or procedure-related death
- Device related infection
- Device related interventions
- Device related hospitalizations
- Fistula failure
- Fistula rupture
- Aneurysm

After the close of the 90-day visit window, all evaluable subjects will be summarized and expansion to a pivotal trial will be requested under a new IDE.

4.2.2 Primary Feasibility (Technical Success):

Rate of Technical Success defined as the successful implantation of the EchoMark implant and the ability to determine blood flow, diameter and depth measurements using the EchoSure diagnostic ultrasound system from baseline to 4 months.

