9.5 Event Assessment and Follow-Up

The occurrence of an adverse event (AE) or serious adverse event (SAE) may come to the attention of study personnel during study visits and interviews of a study participant presenting for medical care, or upon review by a study monitor.

All AEs including local and systemic reactions not meeting the criteria for SAEs will be captured on the appropriate case report form (CRF). Information to be collected includes event description, time of onset, clinician's assessment of severity, relationship to study product, and time of resolution/stabilization of the event. All AEs occurring while on study must be documented appropriately regardless of relationship. All AEs will be followed to adequate resolution.

Any medical condition that is present at the time that the participant is screened will be considered as baseline and not reported as an AE. However, if the study participant's condition deteriorates at any time during the study, it will be recorded as an AE.

Changes in the severity of an AE will be documented to allow an assessment of the duration of the event at each level of severity to be performed. AEs characterized as intermittent require documentation of onset and duration of each episode.

Investigators will record all reportable events with start dates occurring any time after informed consent is obtained until 7 (for non-serious AEs) or 30 days (for SAEs) after the last day of study participation. At study visits, the investigator will inquire about the occurrence of AE/SAEs since the last visit. Events will be followed for outcome information until resolution or stabilization.

The Investigator is to report all SAEs to the study sponsor within 24 hours of first recognition of the event. Additionally, any device malfunctions, failures, and/or explants are to be reported to the sponsor within 24 hours of first recognition of the event.

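### The only relatedness scale (9.4) has overlapping grades and does not separate device from procedure, so scoring of the device-related primary safety composite rests on a CEC charter outside the documents

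*Combined protocol and SAP*

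**What the plan says.** **The scale (9.4).** The rater is the site clinician: "All adverse events (AEs) must have their relationship to study intervention assessed by the clinician who examines and evaluates the participant". There are three grades.

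- *Related* is a list of alternatives, the last of which is "or there is a temporal relationship between the study intervention and event".
- *Possibly Related* asks for some evidence of causality. Its own example is that "the event occurred within a reasonable time after administration of the study device". It then adds: "However, other factors may have contributed to the event".
- *Not Related* is also a list of alternatives, ending "there is no temporal relationship between the study intervention and event onset, or an alternate etiology has been established".

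No order of precedence is given. Section 9.5 lists the items collected for each event as including "clinician's assessment of severity, relationship to study product, and time of resolution/stabilization of the event", which is one relationship item with its object named differently from 9.4.

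**The endpoint (4.2.1).** The primary safety endpoint is the "Composite of new major device related adverse events (MAEs) at 30 days post EchoMark implantation", adjudicated by the CEC. Infection, interventions and hospitalizations carry a device-only qualifier. Death carries a device-or-procedure qualifier. Fistula failure, rupture and aneurysm carry no qualifier of their own, although the composite is headed as device related.

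**The analysis (11.2.6).** The SAP text instead reports the proportion of subjects with device success and no serious adverse event related to device, procedure or both, at 30 days. Section 11.2.8.11 places both formulations side by side for 12 months.

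**The adjudicator (12.7).** The CEC has the final say on safety endpoints and device-related events, under a charter still to be written at its organizational meeting.

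**The concern.** In a single-arm study the composite has no control rate to absorb background events, so the headline result depends on how each event is attributed. Sections 3.1 and 7.4 put the marker in through the same incision and in the same operation as the fistula. Timing therefore cannot tell device from procedure, yet 9.4 treats timing as sufficient for *Related*.

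The object being rated is also unclear. Section 7, headed as the study intervention, includes the operation in which the fistula is created, and Section 8 counts fistula-creation risks among the risks of the research. A clinician cannot tell whether fistula surgery is part of what is being rated or an alternate cause to it. The two readings can send the same wound event to opposite ends of the scale.

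Finally, nothing says whether *Possibly Related* counts as device related. Two competent adjudicators could follow the documents faithfully and report different composite rates. Section 4.2.1 ties the early data summary to a request for a pivotal trial, so the reported rate will be read closely.

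**Working it through.** There is no figure in the plan to reproduce: 11.1 states no null hypothesis, and no safety threshold is given. The check is a logical test of the definitions, followed by the weight of one disputed subject.

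**1. Do the grades exclude one another?** Describe an event by six yes/no facts drawn from 9.4: known to occur with the intervention; reasonable possibility of causation; temporal relationship; some evidence; other contributing factors; alternate etiology established. Two constraints follow from the text: a reasonable possibility implies some evidence, and timing counts as some evidence. Of 2^6 = 64 patterns, those with no evidence but with a reasonable possibility or timing drop out:

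- evidence present: 2^5 = 32 patterns
- evidence absent, so neither reasonable possibility nor timing: 2^3 = 8 patterns
- admissible: 32 + 8 = 40

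Applying the grades literally:

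- *Related* = known, or reasonable possibility, or timing. All 16 patterns with a temporal relationship meet it.
- *Possibly Related* = some evidence and other factors.
- *Not Related* = no reasonable possibility, or no timing, or alternate etiology established. 36 of 40 patterns meet it.
- All three grades at once: 12 of 40.

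These are counts of logical patterns, not event frequencies. They show overlap, not how often it would occur.

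**2. An example.** Take an infection of the shared incision within 30 days, with fistula surgery as a contributing factor.

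- *Related*: met by timing.
- *Possibly Related*: met by reasonable time plus another factor.
- *Not Related*: met only if another cause has actually been established. Whether fistula surgery could serve as that cause depends on whether it is part of the rated intervention, which the text leaves open.

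The event meets two grades on its face, and three if an alternate cause is established.

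**3. Can one rating feed the endpoint?**

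| Where | Attribution needed |
|---|---|
| 4.2.1 infection, interventions, hospitalizations | device |
| 4.2.1 death | device or procedure |
| 4.2.1 failure, rupture, aneurysm | not stated per item |
| 11.2.6 | device and/or procedure, serious events |
| 9.4 | one rating, study intervention |
| 9.5 | one rating, "relationship to study product" |

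A single rating cannot yield both the first and second rows, and the third and fourth do not match the first.

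**4. Weight at n = 20.** Each subject contributes 1/20 = 5 percentage points. Exact (Clopper-Pearson) 95% limits are the 2.5% quantile of Beta(x, n − x + 1) and the 97.5% quantile of Beta(x + 1, n − x):

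| Subjects counted | Rate | 95% interval |
|---|---|---|
| 0/20 | 0% | 0 to 16.8% |
| 1/20 | 5% | 0.1 to 24.9% |
| 2/20 | 10% | 1.2 to 31.7% |
| 3/20 | 15% | 3.2 to 37.9% |
| 4/20 | 20% | 5.7 to 43.7% |

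The number of subjects in dispute is an assumption, shown from 0 to 4. The denominator assumes the full 20 are analysed, without roll-in subjects.

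**The case against.** The strongest reply is that 9.4 does not score the endpoint. It is the site clinician's grading, whereas one central committee adjudicates the composite and device-relatedness (4.2.1, 11.2.6, 12.7). Its charter may contain clear, exclusive definitions. This stands: a reader might infer that the composite cannot be scored consistently, and the documents do not prove that. They show only that they supply no usable rule themselves and do not tell the CEC whether to use 9.4.

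Three other inferences are tempting and not supported.

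- *The scale is inverted, with Related the lower bar.* Timing is also offered as evidence for *Possibly Related*, so the grades overlap rather than invert.
- *The alternate-cause clause would make almost no event device related.* That cause must be established, and 9.4 adds that the product is always to be suspected.
- *Background fistula failure would fill the composite.* The 28 to 36% failed in the literature table of 3.5 is the complement of maturation. Section 7.11 describes failure as a judgement followed by abandonment, and the item sits under a device-related heading. Applying those rates to 20 subjects would not be a forecast.

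The plan also limits the damage. Reinterventions and hospitalizations within 30 days, and any infection to 12 months, are reported without a device qualifier (11.2.8.9, 11.2.8.10). All adverse events are recorded whatever their relationship (9.5). Components are summarized separately and subject listings are provided (11.2.6, 11.2.1). With about 20 subjects a reader can see most events; the ambiguity falls chiefly on the headline composite.

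**Conclusion.** The point holds in this form. The one attribution scale in the documents has overlapping grades, lets timing alone decide *Related*, and does not separate device from procedure. The endpoint in 4.2.1 needs that separation for some components, and 11.2.6 analyses something different. Consistent scoring therefore rests on a charter that is not part of the protocol or SAP.

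The size is 5 percentage points per disputed subject at n = 20. If four subjects were in dispute and there were no other events, the report could read anywhere from 0% (0 to 16.8%) to 20% (5.7 to 43.7%). Four is an illustration, not an estimate, and the 0% end supposes that every one of those events was attributed elsewhere.

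This should be fixed but is not critical. The study is descriptive, states no safety threshold, and already reports some events regardless of attribution. No test, power or sample size changes.

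**What to change.** - **9.4:** remove timing as sufficient for *Related*, make the three grades mutually exclusive, and add a precedence rule.
- **9.4, 9.5 and the event and CEC forms:** record separate relatedness ratings for the EchoMark/EchoSure device and for the fistula creation procedure, by investigator and by CEC. Use one name for the object rated, and state that the CEC uses these definitions.
- **4.2.1, 11.2.6 and 11.2.8.11:** reconcile them so that endpoint and analysis use the same attribution, and carry the result into the synopsis and 4.2.3. State whether *Possibly Related* counts as device related, and show the composite both ways: *Related* only, and *Related* or *Possibly Related*.
- **Fistula failure, rupture and aneurysm:** report all-cause counts beside device-related counts.

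How to count an event that cannot be separated from the procedure is a choice for the sponsor and CEC. It should be written down, since counting all such events as device related could raise the rate by more than a little. The cost is protocol, form and charter wording, one extra rating per event, and possibly a less favourable composite rate.

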9.5 Event Assessment and Follow-Up

The occurrence of an adverse event (AE) or serious adverse event (SAE) may come to the attention of study personnel during study visits and interviews of a study participant presenting for medical care, or upon review by a study monitor.

All AEs including local and systemic reactions not meeting the criteria for SAEs will be captured on the appropriate case report form (CRF). Information to be collected includes event description, time of onset, clinician's assessment of severity, relationship to study product, and time of resolution/stabilization of the event. All AEs occurring while on study must be documented appropriately regardless of relationship. All AEs will be followed to adequate resolution.

Any medical condition that is present at the time that the participant is screened will be considered as baseline and not reported as an AE. However, if the study participant's condition deteriorates at any time during the study, it will be recorded as an AE.

Changes in the severity of an AE will be documented to allow an assessment of the duration of the event at each level of severity to be performed. AEs characterized as intermittent require documentation of onset and duration of each episode.

Investigators will record all reportable events with start dates occurring any time after informed consent is obtained until 7 (for non-serious AEs) or 30 days (for SAEs) after the last day of study participation. At study visits, the investigator will inquire about the occurrence of AE/SAEs since the last visit. Events will be followed for outcome information until resolution or stabilization.

The Investigator is to report all SAEs to the study sponsor within 24 hours of first recognition of the event. Additionally, any device malfunctions, failures, and/or explants are to be reported to the sponsor within 24 hours of first recognition of the event.

The study investigator shall complete an Unanticipated Adverse Device Effect Form and submit to the study sponsor and to the reviewing Institutional Review Board (IRB) as soon as possible, but in no event later than 10 working days after the investigator first learns of the effect. The study sponsor is responsible for conducting an evaluation of an unanticipated adverse device effect and shall report the results of such evaluation to the Food and Drug Administration (FDA) and to all reviewing IRBs and participating investigators within 10 working days after the sponsor first receives notice of the effect. Thereafter, the sponsor shall submit such additional reports concerning the effect as FDA requests.

10. STUDY DISCONTINUATION AND WITHDRAWALDiscontinuation and Closure

This study may be temporarily suspended or prematurely terminated if there is sufficient reasonable cause. Written notification, documenting the reason for study suspension or termination, will be provided by the suspending or terminating party to study participants, investigators, sponsor and regulatory authorities. If the study is prematurely terminated or suspended, the Principal Investigator (PI) will promptly inform study participants, the Institutional Review Board (IRB), and sponsor and will provide the reasoning for the

termination or suspension. Study participants will be contacted, as applicable, and be informed of changes.

Circumstances that may warrant termination or suspension include, but are not limited to:

- Determination of unexpected, significant, or unacceptable risk to participants
- Demonstration of efficacy that would warrant stopping
- Insufficient compliance to protocol requirements
- Data that are not sufficiently complete and/or evaluable
- Determination that the primary endpoint has been met
- Determination of futility

Study may resume once concerns about safety, protocol compliance, and data quality are addressed, and satisfy the sponsor, IRB and/or Food and Drug Administration (FDA).

The DSMB will meet at least every three months to assess the safety and efficacy data of the study. The DSMB will operate under the rules of an approved charter and each meeting must include a recommendation to continue or to terminate the study and whether the DSMB has any concerns about participant safety. Additionally, an emergency meeting of the DSMB may be called at any time by the DSMB chairperson should questions of patient safety arise.

10.2. Withdrawal

Participants are free to withdraw from participation in the study at any time upon request. An investigator may discontinue or withdraw a participant from the study for the following reasons pregnancy, significant study intervention non-compliance, clinical adverse event (AE), laboratory abnormality, or other medical condition or situations such that continued participation in the study would not be in the best interest of the participant.

The reason for participant discontinuation or withdrawal from the study will be recorded on the Case Report Forms (CRFs). Subjects who sign the informed consent form and are randomized but do not receive the study intervention may be replaced. Subjects who sign the informed consent form, and are randomized and receive the study intervention, and subsequently withdraw, or are withdrawn or discontinued from the study, and will not be replaced.

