7.10 Fistula Outside of the EchoMark

If the subject's fistula is deemed to be outside of the EchoMark, an adverse event form will be completed and adjudicated by the CEC. The subject will remain in the study. The EchoSure scans will be suspended. The subject will complete the follow-up schedule as scheduled. Each follow-up visits will include a physical exam, medical history review, Duplex scan, external EchoMark measurement, and adverse event monitoring. The physical exam will include assessing the fistula for bruit and thrill. The medical history will include all interventions, cannulation attempts, and the most recent Kt/V, CBC, Serum Chemistry, Calcium, Phosphorous, Magnesium, Total Protein, Albumin, PTH, Duplex scans will include:

- Depth, Diameter and Volume Flow at/near the EchoMark
- Assessment of patency (flow/no flow adjudicated by the CEC)
- Limited DUS scan performed at the site of EchoMark to determine EchoMark visibility including:
 - 1 BMode, transverse view of EchoMark at center
 - o 1 BMode, transverse view of EchoMark at distal edge
 - 1 BMode, Transverse view of EchoMark at proximal edge
 - 1 BMode, Longitudinal view centered over vessel showing full length of EchoMark
- A duplex exam of the fistula from the EchoMark location and beyond to assess for the presence of stenotic lesions. If a lesion is present, capture and save an image showing a longitudinal view of the fistula segment with the stenosis, note the location of the stenosis in relation to the anastomosis and EchoMark, and track the stenosis as an adverse event.
- A duplex scan of the brachial artery to assess flow and diameter, capture a PW image showing the flow and diameter measurements.

The subject will follow the same 180-day and 12-month visit follow-up visit as described in Section 7.8 7.8 180 Day and 12 Month (+ 15 Days) Follow-up

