7.11 Fistula Failure

If the subject's fistula is deemed a failure and abandoned by the investigator, a fistula failure case report form will be completed recording the reasoning for the failure. The subject will remain in the study and receive monthly telephone calls to monitor for adverse events and physical assessments of the EchoMark at all standard of care visits. The subject will complete the 180-day and 12 months visit as scheduled to undergo a physical exam, medical history review, adverse event monitoring, and duplex examination of the EchoMark and exit the study.

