11.2.10 Handling of Missing Data

Data will only be absent from analyses of study outcomes in the event that they were not available for collection. In general, missing values in any of the endpoints will not be inputted when summarizing these endpoints using descriptive statistics.

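### After an investigator withdraws a subject with the implant still in place, nothing requires new safety events to be collected to 12 months, so the 12-month safety results can be biased low

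*Combined protocol and SAP*

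**What the plan says.** **Withdrawal (section 10.2).** "An investigator may discontinue or withdraw a participant from the study for the following reasons pregnancy, significant study intervention non-compliance, clinical adverse event (AE" opens a list that continues with laboratory abnormality and other conditions or situations. The sentence ends with a condition, "such that continued participation in the study would not be in the best interest of the participant", which can be read as governing the whole list or only its last item. Subjects who receive the intervention "and subsequently withdraw, or are withdrawn or discontinued from the study, and will not be replaced". The section does not separate stopping study scans or visits from ending safety data collection, and it does not mention whether the implant is still in place.

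**After participation ends (section 9.5).** New events are recorded "until 7 (for non-serious AEs) or 30 days (for SAEs) after the last day of study participation". For events already open the rule is different: "Events will be followed for outcome information until resolution or stabilization".

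**Named situations (sections 7.10 to 7.12).** If the fistula lies outside the marker, the EchoSure scans stop but "The subject will remain in the study". If the fistula fails, "The subject will remain in the study and receive monthly telephone calls to monitor for adverse events", and the 180-day and 12-month visits are kept. If the marker is removed, the subject is followed until the event resolves and then exits.

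**Analysis (section 11.2).** The sample is every enrolled subject in whom the marker was successfully implanted (11.2.4), using all available data (11.2.1). On missing data, "missing values in any of the endpoints will not be inputted" (11.2.10). The MAE composite is defined at 30 days in 4.2.1 and at 12 months in 11.2.8.11. The 30-day analysis in 11.2.6 is worded as the proportion with device success and free of related SAEs. No section says how a subject who leaves event-free before 30 days or 12 months enters the numerator or the denominator.

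**The concern.** The exposure here is an implant fixed with non-resorbable sutures, not a treatment that ends when participation ends. Withdrawing a subject for an adverse event, a laboratory abnormality or non-compliance therefore ends most of the observation and leaves the implant where it is. The protocol has a follow-up rule for a displaced fistula, a failed fistula and an explanted marker. It has none for this case beyond the short windows in 9.5.

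The reasons for withdrawal may also be related to the outcome. Section 8 reports infection and seroma from prior use in fistula patients, so an adverse event that leads to withdrawal may be of the kind that the study is meant to count. If such subjects have a higher risk of a later device-related infection, intervention or hospitalization, their 12-month status is missing informatively. With no imputation and no denominator rule, the 12-month MAE composite and the harms listed to 12 months can come out too low.

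**Working it through.** The documents state no figure for withdrawals, and the sample size of up to 20 (11.1) has no hypothesis, power or dropout rate behind it. There is therefore no plan figure to reproduce on this point.

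**Inputs.** Recording windows of 7 days (non-serious) and 30 days (serious) from 9.5; endpoint windows of 30 days and 12 months from 4.2.1 and 11.2.8.11; N = 20 from 11.1. Assumptions: 12 months is 365 days, and the last day of participation is the day of withdrawal, *d*.

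**Step 1: days without capture of new events, 12-month window.** The SAE gap is max(0, 365 − (d + 30)). The non-serious gap is max(0, 365 − (d + 7)).

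| Withdrawal day | SAE gap | Non-serious gap |
|---|---|---|
| 30 | 365 − 60 = 305 | 365 − 37 = 328 |
| 90 | 365 − 120 = 245 | 365 − 97 = 268 |
| 180 | 365 − 210 = 155 | 365 − 187 = 178 |

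The SAE gap closes only for withdrawal from day 335 (335 + 30 = 365), and the non-serious gap from day 358 (358 + 7 = 365).

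**Step 2: the same for the 30-day window.** For SAEs, 30 − (d + 30) is never positive, so the gap is 0 for any withdrawal day from day 1. For non-serious events the gap is max(0, 30 − (d + 7)): 22 days for withdrawal on day 1, 13 on day 10, 3 on day 20 and 0 from day 23. The SAE-based analysis in 11.2.6 is thus covered on paper. The MAE definition in 4.2.1 includes components that need not be serious, such as a device-related infection or intervention, and for these a short gap remains.

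**Step 3: effect on the 12-month proportion.** Assume 1 MAE is observed and 2 of 20 subjects are withdrawn with unknown later status. Exact (Clopper-Pearson) 95% intervals:

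- Withdrawn subjects left out: 1/18 = 5.6% (0.1 to 27.3).
- Withdrawn subjects kept and counted as event-free: 1/20 = 5.0% (0.1 to 24.9).
- Withdrawn subjects kept and counted as events: (1 + 2)/20 = 15.0% (3.2 to 37.9).

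The plan does not say which of these applies. With 1 observed MAE and 1 to 4 subjects withdrawn, the worst case runs from 2/20 = 10.0% to 5/20 = 25.0%, while 1/20 stays at 5.0%.

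**Step 4: direction.** If withdrawn subjects are counted as event-free, every later event that goes unrecorded lowers the rate. If they are left out, the rate is too low only when their later risk exceeds that of the subjects who stay. Withdrawal for an adverse event makes that plausible, but the documents do not establish it.

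**The case against.** Several stronger readings are tempting, and the documents do not support them.

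- A reader might infer that safety observation stops at withdrawal. It does not. Section 9.5 requires open events to be followed and changes in severity to be documented, so a wound problem present at withdrawal that worsens into an infection should still be picked up. The gap concerns events that start later.
- A reader might infer that withdrawn subjects drop out of the results. No text removes them. Under 11.2.1 and 11.2.4 they stay in the sample, and an event before withdrawal counts. What is missing is a rule for those who leave event-free.
- A reader might infer that the 30-day primary result is undermined. Step 2 shows that the exposure is confined to new non-serious components after withdrawal before day 23.
- A reader might infer that 10.2 contradicts 7.10 and 7.11, or that the subjects at highest risk are the ones lost. Section 10.2 is permissive, while 7.10 and 7.11 are specific rules that keep displaced and failed fistulas under observation; the two can coexist. Their relation is only unstated.

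It can also be said that the best-interest condition limits use of the clause, that discontinuations are already summarized with reasons (11.2.2), and that this is a descriptive feasibility study in which the 12-month composite is observational. All of that is fair and limits the weight of the point. None of it supplies 12-month follow-up for new events after withdrawal, or a denominator rule.

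**Conclusion.** The point holds for the 12-month safety results. The plan allows full withdrawal with the implant in place, does not require new events to be collected to 12 months afterwards, and does not say how the resulting incomplete follow-up is counted. The loss is 305, 245 or 155 of 365 days of new-SAE capture for withdrawal on day 30, 90 or 180. In a sample of 20, two subjects of unknown status separate 5.0% or 5.6% from a worst case of 15.0%. These proportions rest on assumed counts of withdrawals and events, and the bias may be nil if nobody is withdrawn under 10.2. For the 30-day result the effect is small. This is an inexpensive improvement to a feasibility plan, not a flaw that invalidates it.

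**What to change.** - **Section 10.2.** Distinguish stopping study scans or visits from ending safety data collection. Leave the investigator's discretion over participation as it is. After investigator-initiated withdrawal with the implant in place, continue to collect adverse events, explant status and fistula status to 12 months by telephone or from records, on the model of the calls in 7.11, unless the subject withdraws consent.
- **Cross-references.** State how 10.2 relates to 7.10, 7.11, 7.12 and the recording windows in 9.5.
- **Section 11.2.** Keep withdrawn implanted subjects in the denominator. Beside each 30-day and 12-month safety rate, report the number withdrawn early and a worst-case count in which those of unknown status are taken as events.

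The cost is one protocol paragraph and a few lines in the analysis section, with the IRB approval that any amendment needs, plus telephone or record checks for the few subjects affected. No new procedure is added and clinical care is unchanged.
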